6.2.3. Efficacy criteria

Complete remission (CR): Completely normal in blood biochemistry test and urine examination;

Partial remission (PR): Urinary protein positive $< (+++)$;

No remission (NR): Urinary protein positive $\geq (+++)$.

6.2.4. Relapse criteria

For 3 consecutive days, morning urinary protein changes from negative to (++) or (+++), or 24hr urinary protein quantification ≥ 50 mg/kg, or urinary protein/creatinine (mg/mg) ≥ 2.0 .

6.3. Safety evaluation

Changes of vital signs: Respiration and heart rate.

Various indexes in laboratory examination: Blood and urine routine examination, liver function, renal function, ECG, chest X-ray examination.

Clinically reported adverse events and adverse reactions.

7. Statistical analysis

7.1. Analysis data set

Full analysis set (FAS): It refers to the set of eligible cases and drop-off cases. The cases are required to have evaluation data after at least one treatment, but excluding the eliminated cases. Per-protocol set (PPS): It refers to the set of cases that meet the inclusion criteria, do not meet the exclusion criteria and complete the treatment plan, that is, the analysis of cases that meet the trial protocol, have good compliance and complete the specified content in CRF (PP analysis).

Safety set (SS): It refers to the actual data with safety index records after receipt of at least one treatment. The missed safety values shall not be carried forward. It includes some eliminated cases that can be evaluated, such as those whose age exceeds the inclusion criteria, but excludes those whose safety judgment cannot be made due to the use of banned drugs. For the incidence of adverse reactions, the number of cases in the safety set is used as the denominator.

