4.3 Elimination criteria

- Those who fail to take the test drugs as required, with a compliance <80% or >120%;
- Those who cannot cooperate well or complete the follow-up as planned, and those who change the drug dose at will;

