11.3.2 Effectiveness analysis

All effectiveness analysis/global indicators will be based on ITT principles, and FAS is adopted, for only the adjudicated endpoint events. The investigators are required to report all the potential endpoint events in eCRF.

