4.5.3. Elimination criteria

- Those who fail to take the test drugs as required, with a compliance <80% or >120%.
- Those who cannot cooperate well or complete the follow-up as planned, and those who change the drug dose at will.

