4.5.5. Drop-out and treatment

4.5.5.1 Definition of drop-out

All patients who have completed the Informed Consent Form and screened to be enrolled in the trial have the right to withdraw at any time. Whenever and for whatever reason, subjects who fail to complete the observation period specified in the Protocol are considered as drop-out cases, including the following situations:

- The subject has serious adverse events and the clinician believes that he/she should withdraw from the clinical trial;
- The subject shows aggravated condition or has other symptoms affecting the trial observation during the trial, and the clinician believes that he/she should withdraw from the clinical trial;
- Important deviations occur in the implementation of clinical trial protocol, such as poor compliance, which would cause difficulty in evaluating the drug effect;
- The subject is unwilling to continue the clinical trial and asks to withdraw from the clinical trial, or loss of follow-up has occurred although no request to withdraw from the trial is proposed.

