8.1.3. Primary efficacy analysis

Logrank test is used for the analysis of relapse-free survival rate which is then used as a covariate for stratification by Sites. HR and its 95% confidence interval (CI) are calculated with Cox proportional hazard model to estimate the efficacy, the confidence interval is applied to verify the superiority of the experimental group and the control group, with a cut-off value of 1 (risk ratio). The model incorporates the same covariate as the Logrank test for fitting, and the definition method of covariates is also the same as that in the Logrank test. The Kaplan-Meier curve of relapse-free survival is drawn by treatment groups. The 1-year relapse-free survival rate and its confidence interval are then calculated.

Calculation rules for the main efficacy indicators:

- If relapse occurred within 9 visits (within 364 ± 7 days) or unscheduled visits within 365 days of randomization, defined as the occurrence of endpoint events. Time of relapse = date of relapse - Random date + 1, calculated by days.
- If the visit stipulated in the protocol was not completed within 9 visits (within 364 ± 7 days) due to loss of follow-up midway or withdrawal or other reasons, it is defined as censoring. Time of

censoring = date of withdrawal - random date + 1, calculated by days.

- If the visit stipulated in the protocol was not completed within 9 visits (within 364 ± 7 days) due to death in the trial, it is defined as censoring. Time of censoring = Death date - random date + 1, calculated by days.
- If the visit stipulated in the protocol was completed and there is no relapse within 9 visits (within 364 ± 7 days), it is defined as censoring. Time of censoring = date of visit 9 (within 364 ± 7 days) - random date + 1, calculated by days.

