9.1. Research overview

Table 1. Distribution of subjects at each site (All enrolled subjects)

Research Site	Group	No. of subjects enrolled	No. of subjects drop-out	Drop-out rate	No. of subjects eliminated	Elimination rate	No. of subjects completed
Site 1	Experimental group						
	Control group						
	Total						
Site 2	Experimental group						
	Control group						
	Total						
...							
Total	Experimental group						
	Control group						
	Total						

Note: 1. The Site name is not displayed in following table, only the site number. Same below. 2. No. of subjects completed = No. of subjects enrolled - No. of subjects drop-out. Elimination refers to subjects who complete the trial, but were not included in the PPS. Subjects who withdrew due to the endpoint event were considered to have completed the trial. 3. Drop-out rate = No. of subjects drop-out / No. of subjects enrolled; Elimination rate = No. of subjects eliminated / No. of subjects enrolled.

Table 2. Distribution of subjects at each site

Site	PPS			FAS			SS		
	Experimental group	Control group	Total	Experimental group	Control group	Total	Experimental group	Control group	Total
Site 1									
Site 2									
Total									

Table 3. Trial completion and distribution of analysis data set (All enrolled subjects)

Items	Indicator	Experimental group	Control group	Total
No. of subjects enrolled	Yes			
	No			
Complete 1 week follow-up	Yes			
	No			
Complete 4 week follow-up	Yes			
	No			
Complete 8 week follow-up	Yes			
	No			
Complete 16 week follow-up	Yes			
	No			
Complete 24 week follow-up	Yes			
	No			
Complete 32 week follow-up	Yes			
	No			
Complete 40 week follow-up	Yes			
	No			
Complete 52 week follow-up	Yes			
	No			
Trial completion	Yes			

Items	Indicator	Experimental group	Control group	Total
	No			
Treatment discontinuation reason	Subject voluntarily withdrew prematurely			
	Decision by the investigator			
	Poor compliance that decided by the investigator			
	Meet the exclusion criteria, or did not meet the inclusion criteria			
	Refusal to continue trial participation			
	Lack of efficacy			
	Adverse events			
	Lost to follow-up			
	Death			
	Other			
FAS				
PPS				
SS				

Note: Follow-up time (years) = (last visit date - random date + 1) / 365.25. Complete 1 week follow-up: follow-up duration \geq 1 week, and so on.

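### The full analysis set is labelled ITT but drops randomised children for adherence and conduct, and elimination has no single definition

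*SAP*

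**What the plan says.** Protocol 11.3.2, repeated in SAP 8.1.2, sets the principle: "All effectiveness analysis/global indicators will be based on ITT principles, and FAS is adopted". Protocol 11.1 and SAP 7.1 define the FAS in two sentences. The first says: "It refers to the set of eligible cases and drop-off cases". The second adds: "The cases are required to have evaluation data after at least one treatment, but excluding the eliminated cases".

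Protocol 4.3 and SAP 4.5.3 are the only sections that list grounds for elimination. The first ground is "Those who fail to take the test drugs as required, with a compliance <80% or >120" (per cent). The second is "Those who cannot cooperate well or complete the follow-up as planned, and those who change the drug dose at will".

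Four other places bear on who is eliminated and who is a drop-out:

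- The drop-out definition (Protocol 4.5.1, SAP 4.5.5.1) includes this situation: "Important deviations occur in the implementation of clinical trial protocol, such as poor compliance, which would cause difficulty in evaluating the drug effect".
- The calculation rules in SAP 8.1.3 deal with a child who misses the planned visits "due to loss of follow-up midway or withdrawal or other reasons, it is defined as censoring", so such children are expected in the primary analysis.
- The note to Table 1 in SAP 9.1 says: "Elimination refers to subjects who complete the trial, but were not included in the PPS". The same note counts children who withdrew because of the endpoint event as having completed.
- The safety-set paragraph in Protocol 11.1 and SAP 7.1 gives over-age children as an example of eliminated cases.

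Table 19 (SAP 9.4.1) reports the primary endpoint for the FAS and the per-protocol set (PPS) only.

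**The concern.** Adherence, cooperation and self-directed dose changes are observed after randomisation, in an open-label trial. They can depend on how a child tolerates the assigned drug or on whether the child relapses. Judging that a family does not cooperate well is partly subjective. Monitoring also differs by arm: the flow chart marks tacrolimus levels at seven visits and mycophenolic acid levels at two. If elimination differs between arms and is related to prognosis, the primary comparison is no longer between the groups that randomisation created.

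The PPS is not an adequate check. The FAS still differs from it by evaluable drop-outs (the plan allows for 15% loss). But a child who completes the trial and is eliminated for adherence or conduct is missing from both sets, so agreement between them says nothing about this selection.

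The wording also leaves the primary dataset undetermined. Two programmers following the SAP could build different FAS populations from the same data.

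**Working it through.** **1. The plan's own figures.** Protocol 3.3.2 and Appendix 4 assume 1-year relapse-free survival (RFS) of 0.56 on MMF and 0.70 on tacrolimus.

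- HR = ln 0.70 / ln 0.56 = 0.615 (stated 0.6151); difference 0.140.
- 229 / 0.85 = 269.4, rounded up to 270, or 135 per arm. The 15% loss is 270 × 0.15 = 40.5 children.

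These reproduce, so the point does not rest on a sample-size error. The 15% is an allowance for loss to follow-up and does not mention eliminations.

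**2. Who leaves the FAS under each meaning of elimination.**

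| Meaning | Consequence |
|---|---|
| Protocol 4.3 / SAP 4.5.3 | Children with poor adherence or conduct leave the primary set. Those with incomplete follow-up are removed by this rule, yet kept as drop-outs by SAP 7.1 and censored by SAP 8.1.3. |
| Table 1 note | Every completer outside the PPS leaves, so the FAS is roughly the PPS plus drop-outs. A non-adherent child who withdrew at relapse counts as a completer, so an observed relapse can leave the primary analysis. |
| Safety-set text | Over-age children, a baseline fact, also count as eliminated. This appears in neither of the other two definitions. |

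No meaning gives an ITT set, and no rule says which one prevails.

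**3. Possible size (assumptions).** The documents give neither an elimination rate nor a prognosis for eliminated children. Let S be the arm's true RFS, p the fraction eliminated and Sx the RFS of those eliminated. The RFS that remains is (S − p·Sx)/(1 − p), and HR = ln(S tacrolimus)/ln(S MMF).

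Example with Sx = 0.30: MMF at p = 0.05 gives (0.56 − 0.015)/0.95 = 0.574. Tacrolimus at p = 0.15 gives (0.70 − 0.045)/0.85 = 0.771.

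Scenario A sets Sx = 0.30 in both arms. Scenario B keeps the design HR among eliminated children, so Sx is 0.30 on MMF and 0.30^0.615 = 0.477 on tacrolimus.

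| Eliminated, MMF / tacrolimus | A: difference (HR) | B: difference (HR) |
|---|---|---|
| 5% / 15% | 0.197 (0.47) | 0.166 (0.54) |
| 15% / 5% | 0.115 (0.65) | 0.106 (0.68) |
| 10% / 10% | 0.156 (0.56) | 0.136 (0.61) |

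Against 0.140, the shift is −2.5 to +5.7 points in A (−1.2 to +4.5 if Sx = 0.40) and −3.4 to +2.6 points in B.

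**4. Milder and neutral cases.** Let eliminated children have m times their arm's relapse risk r. The risk that remains is r(1 − p·m)/(1 − p).

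- m = 1.5: HR 0.571 with 5%/15% elimination and 0.674 with 15%/5%.
- m = 2.0: HR 0.526 and 0.743.
- m = 1.0: HR stays at 0.615. With 135 per arm and one year of follow-up, expected events are 135 × (0.44 + 0.30) = 99.9. At 15% elimination per arm they fall to 99.9 × 0.85 = 84.9.

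**5. No true difference.** The simulation used 10,000 trials per case, 135 per arm, exponential relapse times, censoring at one year, RFS 0.63 in both arms (midpoint of 0.56 and 0.70), eliminated children at 0.30, and an unstratified two-sided log-rank test at 5%.

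| Eliminated | Rejection after elimination | All randomised kept |
|---|---|---|
| 5% / 15% | 10.2% | 5.1% |
| 5% / 10% | 6.3% | 5.0% |
| 10% / 10% | 5.1% | 5.0% |

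The simulation standard error near 5% is √(0.05 × 0.95/10,000) = 0.2 points. A normal approximation for 5%/15% elimination gives about 6.6% at m = 1.5 and 12% at m = 2.0.

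**The case against.** The best defence is that elimination was meant as a PPS concept and the FAS clause is a drafting slip. The Table 1 note defines elimination by absence from the PPS, and Table 110 asks for a reason only for exclusion from the PPS. That is plausible, but the FAS definition still removes these children, and a programmer would follow it.

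Some limits on the point do stand:

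- The overlap on poor compliance can be partly resolved. A poor complier who leaves early could be a drop-out and one who completes could be eliminated. The incomplete-follow-up conflict cannot be resolved that way.
- Many dose changes are not eliminations. Reductions for tolerability are directed by the protocol, and a child off protocol dosing for 14 consecutive days must withdraw and so may count as a drop-out. This narrows the pool, and 15% in one arm may be high.
- Differential elimination would be visible in Tables 1, 2, 108 and 110. These tables show counts and adherence. They do not give a relapse estimate with the eliminated children restored.
- Scenarios A and B and the simulation all assume that eliminated children do worse, and the largest effects need a threefold imbalance between arms. The simulation also ignores site and drop-out. The neutral case in step 4 shows no bias.

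**Conclusion.** The concern holds. The primary population is called ITT, but its definition removes randomised children for behaviour after randomisation, and nothing elsewhere in either document repairs this. That conclusion rests on the text alone.

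The direction and size of any bias are unknown. Under an assumed 5%/15% imbalance in either direction, with eliminated children doing worse, the expected HR moves from 0.615 to somewhere between 0.47 and 0.74. With no true effect, the false-positive rate rises to about 7-12%. With equal elimination the false-positive rate stays near 5%, although the estimated difference can still shift (0.156 in scenario A). With elimination unrelated to prognosis only events are lost.

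This must be corrected before the primary analysis, because the analysis set is both mislabelled and not uniquely defined.

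**What to change.** 1. In Protocol 11.1 and SAP 7.1, delete the clause that excludes eliminated cases. Define the FAS as all randomised children analysed in their assigned group, at most leaving out those with no study drug and no post-baseline relapse assessment.
2. Apply the elimination criteria to the PPS only.
3. Give elimination and drop-out one definition each. Reconcile Protocol 4.3, 4.5.1 and 11.1 with SAP 4.5.3, 4.5.5.1, 7.1, 8.1.3 and the Table 1 note.
4. State that relapses in randomised children who were non-adherent or over age count in the FAS. The over-age part follows from the ITT principle, not from the calculations above.
5. As a secondary point, the safety set drops treated children whose safety cannot be judged because of banned drugs, although it is the denominator for adverse reactions. Define it as all children who took at least one dose, and list banned-drug users separately.

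The cost is wording; no new data are needed. Protocol 12.1 requires ethics approval before a revision is implemented. SAP 4.1 describes enrolment as already completed, so the amendment should be dated and justified. Including non-adherent children may dilute the estimated effect; the PPS result remains for the adherent population.

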4.2. Design principle and case allocation

4.2.1 Difference analysis

In this research, Logrank method is used to compare the difference of 1-year relapse-free survival between the two groups.

[figure not shown]
Eligible patients will be randomly divided into FK506 Group or MMF Group at the ratio of 1:1. The random codes are generated by the computer and the random envelopes are made according to these random codes. Grouping information is attached in each envelope. Each code is provided with a corresponding random envelope, and the random numbers are given to the subjects from small to large according to the time sequence when the subjects meet the inclusion criteria. The

corresponding random envelopes can only be opened when grouping. Any random number falling off midway after use cannot be used again.

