4.2.2 Determination of the number of cases

It is estimated that 1-year relapse-free survival is 0.56 in MMF Group, and 0.70 in FK506 Group. The enrollment time of this research is expected to be 2 years, and the total time of this research is 3 years, with a test level $\alpha = 0.05$, and a power of test $1 - \beta = 80\%$. It is estimated to have 114 patients in MMF group and 115 patients in FK506 group, with a total of 229 patients. With the consideration of 15% loss of follow-up, a total of 270 patients are needed, including 135 patients in each group.

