7.2. General considerations of date analyses

7.2.1. General Statistical methods

SAS 9.4 software is adopted for Statistical analysis. Two-sided test is adopted for all Statistical tests. If the P value is less than 0.05, the tested difference will be considered "Statistically significant" (unless otherwise specified).

Descriptive analysis: Sort out and summarize a large number of data obtained from the survey to find out the internal law of these data - centralized trend and decentralized trend. Single factor analysis is mainly carried out with the help of statistics represented by various data, such as mean and percentage.

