9.4. Efficacy analysis (FAS/PPS)

9.4.1. Primary efficacy indicators: 1-year relapse-free survival rate

Table 19. 1-year relapse-free survival analysis

Items	Indicator	FAS		PPS	
		Experimental group	Control group	Experimental group	Control group
1-year recurrence time (days)	N (Missing)				
	Endpoint event (%)				
	Censoring (%)				
	Median survival time				
	95%CI				
	Q1, Q3				
	Log-rank test				
	P-value				
Cox regression analysis	Hazard Ratio				
	95%CI				
	Wald chi-square				
	P-value				

Note: The independent variables of Cox regression analysis are group and Site. Same below.

Figure 1. 1-year relapse-free survival analysis chart (FAS)

Figure 2. 1-year relapse-free survival analysis chart (PPS)

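### The PPS rule can keep children who exit at relapse while deleting those who leave relapse-free, so the supportive PPS hazard ratio can be biased if the arms lose children at different rates

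*SAP*

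**What the plan says.** SAP 7.1 (and Protocol 11.1, with the same definition) admits to the PPS children who satisfy the inclusion criteria, "do not meet the exclusion criteria and complete the treatment plan", with good compliance and a complete CRF.

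Three other places bear on who counts as having completed:

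- SAP 9.1, notes to Table 1: completed equals enrolled minus drop-outs, and elimination means a completer who is left out of the PPS. The same notes add: "Subjects who withdrew due to the endpoint event were considered to have completed the trial".
- SAP 4.5.5.1: any child who does not finish the observation period, for whatever reason, is a drop-out.
- SAP 8.1.3: a child who withdraws or is lost before relapse is censored at withdrawal.

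SAP Table 19, titled "1-year relapse-free survival analysis", gives the log-rank test and Cox HR for the FAS and the PPS side by side, and Figure 2 is the PPS curve. Tables 20 to 22 and Figure 4 also use the PPS. SAP 8.1.2 assigns effectiveness analysis to the FAS.

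**The concern.** If Table 1 defines completion for SAP 7.1 too, PPS membership depends partly on the outcome. A child who exits because of relapse contributes an event. A child who leaves at the same time without relapse contributes nothing. The censoring rule in SAP 8.1.3 cannot repair this, because it acts only on children still in the set.

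Deleting only event-free follow-up raises the apparent relapse rate in each arm, and raises it more in the arm with more leavers. Unequal loss is plausible. Withdrawal is required when a target concentration is not reached after adjustment, or on a creatinine and eGFR criterion (SAP 4.5.4). The Protocol flow chart schedules tacrolimus levels at seven visits and mycophenolic acid at two. The trial is open-label.

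Readers will take agreement between the FAS and PPS columns of Table 19 as evidence of robustness, and disagreement as a warning. Either could reflect who left rather than how the drugs performed.

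**Working it through.** **Inputs from the documents.** SAP 4.2.2 assumes that "1-year relapse-free survival is 0.56 in MMF Group, and 0.70 in FK506 Group", with 15% loss overall (not split by arm) and 135 children per arm. Tests are two-sided at 0.05 (SAP 7.2.1), and each child is observed for 1 year (SAP 4.1).

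**Plan's own figures.** HR (FK506 over MMF) = ln 0.70 / ln 0.56 = 0.6151, as in Protocol Appendix 4. With exponential relapse, 2-year uniform accrual and 3 years in total, expected events are 76.2 + 57.4 = 133.7 (stated 133.8) and power is 0.802 (stated 0.8009). 229 / 0.85 = 269.4, rounded up to 270. The inputs are confirmed.

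**Model.** Relapse hazard is λ = −ln(1-year relapse-free rate). Independent leaving has hazard c = −ln(1 − loss). Let p be the share of relapsers who exit at relapse; the others must stay to Visit 9 to count as completers. The chance of being in the PPS is then:

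- relapse-free child: exp(−c)
- child relapsing at time t: p·exp(−ct) + (1 − p)·exp(−c)

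The second exceeds the first whenever p > 0 and c > 0. At p = 0 they are equal, so independent loss leaves the HR unchanged. At p = 1 every child who relapses before leaving is kept, which is the largest effect for a given loss split.

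**Equal 15% loss, p = 1.** The fraction kept is λ/(λ+c)·(1 − exp(−(λ+c))) + exp(−(λ+c)).

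- MMF: λ = 0.580, c = 0.163, exp(−(λ+c)) = 0.56 × 0.85 = 0.476. Kept = 0.781 × 0.524 + 0.476 = 0.885. PPS 1-year rate = 0.476 / 0.885 = 0.538.
- FK506: λ = 0.357, 0.70 × 0.85 = 0.595. Kept = 0.687 × 0.405 + 0.595 = 0.873. PPS rate = 0.595 / 0.873 = 0.681.

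The rates fall from 0.56 and 0.70 to 0.538 and 0.681. The HR barely moves, from 0.615 to 0.619.

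**Unequal loss, p = 1.** The splits are assumptions around the plan's 15%. HRs are large-sample Cox limits. The null sets both arms at 0.63. Rejection rates come from 4,000 simulated trials of 135 per arm.

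| Loss MMF / FK506 | PPS HR, true HR 1 | PPS type I error | PPS HR, true HR 0.615 | PPS power | Power, leavers censored |
|---|---|---|---|---|---|
| 10% / 20% | 1.057 | 5.1% | 0.654 | 50% | 63% |
| 20% / 10% | 0.947 | 5.9% | 0.586 | 73% | 64% |
| 5% / 25% | 1.117 | 8.4% | 0.691 | 42% | 63% |
| 25% / 5% | 0.896 | 8.3% | 0.554 | 81% | 64% |

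Repeat simulations put type I error at about 6 to 7% for the 10-point gap and 8 to 9% for the 20-point gap, and extended the power range down to 41%. With leavers censored, the HR limit is 1.00 or 0.615 in every row.

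**Smaller p, 5% v 25% loss.** At p = 0.5 the null HR is about 1.06 when FK506 loses more. At p = 0.25 it is about 0.97 or 1.03, and the HR at the design effect is 0.60 to 0.64. At p = 0 it is 1.00.

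**The case against.** **The rule is inferred.** SAP 7.1 does not say that children who exit at relapse stay in the PPS, or that every drop-out is removed. The link runs through a note to a disposition table, and assumes that a trial completer in that note satisfies the treatment-plan condition. Table 109 lists drop-outs with a PPS flag and a reason for non-inclusion, so case-by-case assignment is possible. This stands, and the SAP should settle it.

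**Many relapsers will not exit.** SAP 5.2.2 treats relapse within the trial with the study drug dose unchanged, and relapse is not a listed withdrawal criterion. The Table 1 note covers only exits due to the endpoint. A relapsed child who stays and later leaves for another reason is also a drop-out. This stands too, and makes the p = 1 figures an upper bound for each split. A reader might infer that the PPS HR is biased whenever loss is unequal. The documents do not support that: at p = 0 there is no HR bias, and even at p = 1 one unequal pair cancels at the design effect (MMF 15%, FK506 about 14.0%).

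**The splits are assumed.** Nothing in the documents supports a five-fold difference in loss. At 10% v 20%, type I error stays near nominal even at p = 1.

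**The power range needs its reference.** A reader might set 41% against the planned 80% and blame the PPS for the whole gap. With leavers censored, power is already only about 64%: one year per child gives 135 × 0.44 + 135 × 0.30 = 99.9 events before loss, against the 133.8 planned. Sample size is a separate matter.

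**The PPS is supportive.** A reader might infer that the primary result is compromised. This rule does not reach it: the FAS definition includes drop-off cases, and SAP 8.1.3 censors them.

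**Conclusion.** The concern holds as a conditional defect of a supportive analysis. If the Table 1 note governs completion in SAP 7.1, PPS membership depends partly on relapse, and the PPS results in Table 19 and Figure 2 can be biased against the arm that loses more children.

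The upper bound, with all relapsers kept, is a null HR of about 0.95 or 1.06 at a 10-point gap in loss and 0.90 or 1.12 at a 20-point gap. At the design effect it is a PPS HR of about 0.55 to 0.69 and power of about 41% to 81%. The bias shrinks to about 3% of the null HR at a 20-point gap if a quarter of relapsers exit at relapse, and to nothing if none do. With equal loss the HR is essentially unaffected, although the PPS 1-year rates are too low whenever some relapsers exit at relapse.

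These sizes rest on exponential relapse, independent leaving, assumed splits of the 15% loss and an unknown exit share. The direction and the mechanism do not depend on the particular figures chosen.

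**What to change.** In SAP 7.1 and Protocol 11.1, define the PPS by absence of major protocol deviations up to the first of relapse, exit or Visit 9, rather than by completing the year. Keep relapse-free early leavers who had no major deviation, censored as SAP 8.1.3 already provides. If a completer-type set is retained instead, state whether completer status in the Table 1 notes counts towards the PPS, and report loss by arm and the number who exit at relapse beside Table 19.

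The change is about one sentence in each document and needs no new data. Its cost is that the PPS will include children with shorter exposure. It recovers the true HR only if leaving is unrelated to relapse risk, which is the same assumption the FAS analysis makes when it censors leavers.
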